2.2 Outcomes

- Primary Outcome: MS Work Instability Scale (MS WIS) at 6 months after randomisation: 22-item, self-administered scale measuring work instability.
- Secondary outcomes: Health related quality of Life (EQ-5D, SF-12), mood (HADS), self-efficacy (Uni-dimensional Self-efficacy Scale for Multiple Sclerosis - USE-MS), impact of MS (Multiple Sclerosis Impact Scale-29, MSIS-29), fatigue (Neurological Fatigue Index for multiple sclerosis - NFI-MS), psychological flexibility (Comprehensive assessment of Acceptance and Commitment Therapy processes -

CompPACT), participant satisfaction with the technology post-intervention (system usability scale - SUS).

3 STUDY DESIGN and METHODS of DATA COLLECTION AND DATA ANALYSIS

DESIGN: This is an external pilot trial. The main purpose is to assess the efficacy of the new online version of READY for MS. The process evaluation will assess the methods of recruitment, randomisation and follow up for a future full trial. The trial is a two centre, two-arm individual patient randomised control trial. We plan to recruit people with a confirmed diagnosis of MS in paid employment attending regional outpatient MS clinics in Leeds and London. The planned follow up is 6 months post-intervention.

SETTING: Recruitment from outpatient MS clinics in 2 regional NHS MS centres. The intervention will be self-managed flexibly in the home setting.

CENTRES: Leeds Teaching Hospitals NHS Trust (CI HF) and Queen Square MS centre, University College London (Co-I WB).

TRAINING: We will hold a training workshop on 'READY for MS' in Leeds for the investigators and the MS Specialist Nurses from the two recruiting centres.

RANDOMISATION: 1:1 by patient. Randomisation will be managed by an independent statistician.

INTERVENTION: The intervention to be tested is the digital version of the READY for MS group programme ([name] et al., 2018) adapted for the UK setting. This will be used with standard care with a written information leaflet about employment and MS 'Work and MS: An employee's guide' (MS Society, 2015).

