ANALYSIS: The primary outcome will be analysed using a linear mixed model, including assessments at all available time points (baseline, 8 weeks and 6 months) and include as fixed effects: trial arm, time, arm by time interaction and other important baseline covariates with participant treated as a random effect to account for the repeated measures within subjects.

TIMELINE: MS-PROACTIVE duration - 24 months: Adaptation of the intervention and trial setup - 6 months; Recruitment and randomisation - 6 months; RCT follow up - 6M; data analysis & report writing - 6 months.

All personal and patient identifiable data will be processed in accordance with the European Union General Data Protection Regulation (GDPR) and the UK Data Protection Act 2018.

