5.2.2 Sampling technique

We aim to recruit people with a confirmed diagnosis of MS in paid employment. We plan to use the MS Work Instability Scale (MS-WIS) as a screening tool to identify subjects with medium or high levels of work instability (WI). In the baseline population from the longitudinal study of 208 PwMS 20.2% had high WI, 37.0% had medium WI and 42.8% had low WI. (Wicks et al., 2016).

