6 ETHICAL AND REGULATORY CONSIDERATIONS

People with MS lose their jobs much earlier than expected. This can be due to complex factors including psychological factors. Self-efficacy has been found to be a key factor in staying in work.

The aim of this pilot study is to test an online version of a type of Acceptance and Commitment Therapy (ACT) called READY for MS. This has been developed and tested in Australia.

This project meets one of the MS Society's Top 10 James Lind Alliance priorities: How can people with MS be best supported to self-manage their condition?

Recruitment:

We plan to recruit from the outpatient MS clinics at Leeds Teaching Hospitals NHS Trust and University College London. We will explain to PwMS that this is a small study called a pilot trial. They may have no personal benefit at all from taking part in the study. If the study is successful it may lead to a much larger trial of READY for MS.

We have previous experience in Leeds of recruiting over 200 employed PwMS to a previous MS Society funded project grant. This required the completion of questionnaires at 4 time points over 2 years. We had a very impressive response rate at each time point of 96%, 94%, 91% and 88%.

Inclusion and Exclusion criteria:

To be included in the trial people need to have a confirmed diagnosis of MS and currently be in paid employment (full-time, part-time or self-employed). We plan to screen PwMS with a short screening questionnaire called the Work Instability Scale. This measures the level of work instability as no/moderate or high. Work instability measures the potential risk of job loss. Participants with moderate or high work instability will be invited to be randomised in the trial. Those with no work instability will not be included in the

IRAS 279736

trial. The reason for this is that the trial is measuring work instability as the main outcome with an aim to show improvement.

PwMS who are currently working on a voluntary basis or in an unpaid role will not be eligible for the trial.

PwMS who are planning to fully leave work or retire before the end of the trial will be excluded.

Consent

PwMS who are currently employed will be approached by their clinical MS team including the MS Specialist nurses and MS specialist neurologists. The clinical team will introduce the study to the potential participants.

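### The primary model treats baseline MS-WIS as an outcome with a free arm effect, so the 6-month contrast is unbiased but not efficiently adjusted for baseline

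*Protocol*

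**What the plan says.** The primary outcome (Section 2.2) is the "MS Work Instability Scale (MS WIS) at 6 months after randomisation". The ANALYSIS paragraph of Section 3 specifies a linear mixed model "including assessments at all available time points (baseline, 8 weeks and 6 months"), so baseline is one of three responses. The model will "include as fixed effects: trial arm, time, arm by time interaction and other important baseline covariates with participant treated as a random effect". Four things are not stated:

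- any constraint that the arms share a baseline mean;
- baseline MS-WIS as a covariate;
- the residual covariance;
- which coefficient, or combination of coefficients, is the 6-month effect.

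The same scale also selects participants. Section 5.2.2 says "We plan to use the MS Work Instability Scale (MS-WIS) as a screening tool to identify subjects with medium or high levels of work instability", and Section 6 adds that "Participants with moderate or high work instability will be invited to be randomised in the trial". In the earlier cohort of 208 cited in Section 5.2.2, 42.8% had low work instability and would have been screened out.

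**The concern.** In a model with free arm, time and arm-by-time effects and baseline among the responses, the arm term estimates a baseline difference that randomisation already sets to zero in expectation. Two 6-month contrasts can be read off. Arm plus interaction is, with complete data, the raw difference in 6-month means. The interaction alone is the difference in change from baseline. The first makes no use of baseline, and the second subtracts all of it. An analysis that adjusts for baseline, or constrains the baseline means to be equal, weights baseline by its actual correlation with the outcome and is more precise.

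Section 3 gives efficacy as the main purpose, and Section 5.2.1 counts on about 70 measured participants, so the precision of this contrast matters. Selection on the MS-WIS adds a second question. It narrows the baseline spread relative to follow-up, and a model that assumes equal variance at every visit would then misstate the 6-month variance.

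**Working it through.** **The plan's own figures.** The 95% half-widths are 1.96 × √(0.5 × 0.5/176) = 7.4% and 1.96 × √(0.2 × 0.8/88) = 8.4%. Also 176 × 0.5 = 88 and 88 × 0.8 = 70.4. These reproduce Section 5.2.1. The protocol gives no SD, visit correlation, effect size, alpha or power, so there is no planned precision for the arm contrast to reproduce.

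**Inputs.** From the documents: 88 randomised 1:1 (44 per arm), three visits, 42.8% screened out. Assumed: normal scores with unit variance at every visit before selection; equal correlation ρ of 0.5 to 0.7 between visits; two-sided 5% tests; the screening score serving as baseline; complete data for the closed forms.

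**Step 1: baseline variance after screening.** For a normal score cut at its 42.8th percentile, a = −0.18 and λ = φ(a)/0.572 = 0.686. Then V0 = 1 + aλ − λ² = 0.405.

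**Step 2: follow-up moments.** V6 = 1 − 0.595ρ² and C06 = 0.405ρ.

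**Step 3: variances, each to be multiplied by 2/44.** Raw difference: V6. Change: V6 + V0 − 2C06. Baseline-adjusted: V6 − C06²/V0 = 1 − ρ².

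| ρ | Raw | Change | Adjusted | Raw/adjusted | Change/adjusted |
|---|---|---|---|---|---|
| 0.5 | 0.851 | 0.851 | 0.750 | 1.13 | 1.13 |
| 0.6 | 0.786 | 0.705 | 0.640 | 1.23 | 1.10 |
| 0.7 | 0.708 | 0.546 | 0.510 | 1.39 | 1.07 |

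The excess variance is 7% to 39%. For scale, 70 measured participants would give the precision that baseline adjustment gets from 70/1.39 = 50 to 70/1.07 = 65.

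If baseline were not range-restricted, the ratios would be 1/(1 − ρ²) = 1.33 to 1.96 (raw) and 2/(1 + ρ) = 1.33 to 1.18 (change). In simulation with 20% missing at 6 months (3,000 runs per setting), the excess was 8% to 30% (raw) and 6% to 12% (change). If baseline is a separate administration correlating 0.8 with screening, it was 12% to 38% and 17% to 22%.

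**Step 4: standard error, only if the fit is a random intercept with equal residual variance.** Such a fit uses the average visit variance, (V0 + V8 + V6)/3, where V8 = V6 under equal correlations. This gives 0.702, 0.659 and 0.607. For the raw difference, model SE/true SE is:

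- ρ = 0.5: √(0.702/0.851) = 0.91
- ρ = 0.6: √(0.659/0.786) = 0.92
- ρ = 0.7: √(0.607/0.708) = 0.93

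Type I error is 2[1 − Φ(1.96 × ratio)] = 7.5%, 7.3% and 7.0%. Simulations with 20% missing gave 6.4% to 7.6%.

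For the change contrast under the same assumptions, the ratios are 1.029, 1.022 and 1.016, so its SE is about 2% to 3% too large. If correlation instead decays with time (adjacent visits 0.6 to 0.8, baseline to 6 months 0.49 to 0.65), the change-contrast ratio falls to 0.86 to 0.96.

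**The case against.** The strongest defence is that this is a standard longitudinal model. It is unbiased under randomisation and keeps every randomised participant with any score, which matters because Section 3 itself expects attrition with online treatment. That stands: the issue is efficiency, not bias.

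It can also be said that residual covariance, covariates and the reported contrast belong in the SAP, which the trial management group's duties show was planned. That stands for the covariance. It does not rescue the fixed part, because the protocol itself puts baseline on the response side with a free arm effect. Adding baseline MS-WIS under the unnamed covariates would put it on both sides of the model.

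Two stronger readings are tempting, and the documents do not support them.

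- **A reader might infer that the confidence interval is too narrow and type I error exceeds 5%.** The protocol does not state equal residual variance across visits; a participant random effect is compatible with visit-specific variances. Sections 3, 5.2.2 and 6 do not say that the screening and baseline scores are one administration. With a separate administration correlating 0.8, simulated type I error was 5.3% to 6.2%. With a Monte Carlo error of about 0.4 points, the lower end cannot be told from 5%.
- **A reader might infer that a pooled model variance will feed the definitive trial's sample size.** Section 5.2.1 refers only to the standard deviation of the outcome measure.

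**Conclusion.** The point holds as a loss of precision. As written, the model gives a 6-month effect that is unbiased but not efficiently adjusted for baseline. Its variance is about 7% to 40% larger than need be. That size rests on assumed correlations of 0.5 to 0.7, normal scores and the screening cut-off taken from the earlier cohort. The direction does not depend on those values for correlations in this range.

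The understated standard error (about 7% to 9%, type I error about 7%) is a risk, not an established fault. It requires equal residual variance, the screening score as baseline, and the raw 6-month difference as the reported contrast. With equal correlations it does not reach the change contrast.

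For an external pilot with no stated test threshold the consequence is moderate. It is still worth correcting, because efficacy is given as the main purpose and the remedy is nearly free.

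**What to change.** Reword the ANALYSIS paragraph in one of two ways:

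- **Baseline as covariate:** model 8-week and 6-month MS-WIS as responses, with baseline MS-WIS as a covariate and fixed effects for arm, time and arm by time.
- **Constrained baseline:** keep all three visits as responses, but constrain the arm means to be equal at baseline.

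In either case, use an unstructured covariance so that variances may differ by visit. Name the adjusted arm difference at 6 months, with its 95% CI, as the primary contrast. State also whether the screening MS-WIS serves as the baseline score.

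The cost is a sentence or two in the protocol and SAP, using data already planned. The covariate version drops participants with no post-baseline score. They carry little information on the contrast, and the constrained version keeps them.

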4 STUDY SETTING

4.1 Recruitment

Recruitment to the study will be from outpatient MS clinics or day case units in two regional NHS MS centres: Leeds Teaching Hospitals NHS Trust (CI HF) and Queen Square MS Centre, University College London (Co-I WB).

The outpatients department and day-case units will be the same locations which patients routinely attend for their regular clinical visits and will be a familiar environment for the participants. Potential participants will be given at least 48 hours to consider the study and will then be asked if they wish be enrolled in the study.

4.2 Intervention

The intervention will be self-managed flexibly in the home setting. The primary and secondary outcome measures are questionnaires and can be completed at home.

5 SAMPLE AND RECRUITMENT

5.1 Eligibility Criteria

5.1.1 Inclusion criteria

- Age above 18 years at the time of enrolment into the study
- Participants with a confirmed diagnosis of MS
- Participants are in paid employment including full-time, part-time or self-employed
- Participants must be able to comply with the terms and methods of the protocol
- Study specific written informed consent obtained

5.1.2 Exclusion criteria

- Age below 18 years at the time of enrolment into the study
- Participants who are planning to retire or fully leave employment in the time period of the randomised controlled external pilot trial
- Participants unable to comply with the terms or methods of the protocol, in particular the completion of the online sessions of READY for MS and completion of the questionnaire outcome measures

5.2 Sampling

5.2.1 Size of sample

This study aims to recruit 88 PwMS who are in paid employment and have medium or high work instability to participate in the randomised controlled pilot trial.

The sample size calculations are based on estimating participation and attrition rates and standard deviation of the primary outcome. If we identify 176 eligible subjects, we will be able to estimate a

participation rate of 50% to within a margin of error of $\pm 7\%$ and an attrition rate of 20% to within $\pm 8\%$

(Hertzog, 2008). Furthermore, an external feasibility study of at least 70 measured subjects will provide robust estimates of the standard deviation of the outcome measure to inform the sample size calculation for the subsequent larger definitive fully powered trial (Teare et al., 2014).

5.2.2 Sampling technique

We aim to recruit people with a confirmed diagnosis of MS in paid employment. We plan to use the MS Work Instability Scale (MS-WIS) as a screening tool to identify subjects with medium or high levels of work instability (WI). In the baseline population from the longitudinal study of 208 PwMS 20.2% had high WI, 37.0% had medium WI and 42.8% had low WI. (Wicks et al., 2016).

5.3 Recruitment

5.3.1 Sample identification

Potential study participants will be approached by the clinical MS teams in person or over the phone. This will include identification by specialist consultant neurologists, neurology trainees working in the MS clinics, MS clinical nurse specialists, MS physiotherapists, occupational therapists and neuropsychologists. All are directly involved in the clinical care of PwMS.

There are a large population of employed PwMS attending the outpatient services and day-case units in both of the recruiting centres. There are 1,080 PwMS registered on the Leeds MS register. As this is a small pilot study, we don't anticipate significant problems in recruitment. The Leeds site has previously recruited 200 employed PwMS to a longitudinal questionnaire study over 3 years with excellent retention rates.

The eligibility criteria of the study will be disseminated to the clinical team, in order for them to be able to identify potential participants for the study. The participants will be informed of the study briefly and if

IRAS 279736

interested they will be asked if their details can be given to the research team to provide the participant information sheet (PIS) of the study.

We will not use adverts or websites for recruitment purposes. The participants will not receive any financial incentives to participate in the study.

5.3.2 Consent

Consent will be obtained by the lead clinical investigator at each site: this will be the Chief Investigator in Leeds (HF) and the Consultant Neurologist Co-Investigator in London (WB).

Participants will be provided with a written patient information sheet by the research team.

Once potential participants have been identified, the Chief investigator or Co-Investigator will discuss the study with the potential participant and any relatives/carers the participant would like to be made aware. The verbal discussion will include a detailed description of the objectives and schedule of the study as well as what is required of the participant. The investigator will explain the benefits and possible risk of taking part in the study.

During the initial meeting, the investigator will make an assessment of the participant's capacity to consent to take part in the study. The participant's understanding of the study, their role in the study, as well as their ability to retain the information will be assessed. After the potential participant has received all the relevant information on the study and wants to be involved in the study, they will then receive the consent form which will be completed before any study specific activity takes place. The consent form will be countersigned by the chief investigator or the study co-investigator. A copy of the PIS and completed consent form will be retained by the participant and the original copy of the consent form will be filed in the site file.

6 ETHICAL AND REGULATORY CONSIDERATIONS

People with MS lose their jobs much earlier than expected. This can be due to complex factors including psychological factors. Self-efficacy has been found to be a key factor in staying in work.

The aim of this pilot study is to test an online version of a type of Acceptance and Commitment Therapy (ACT) called READY for MS. This has been developed and tested in Australia.

This project meets one of the MS Society's Top 10 James Lind Alliance priorities: How can people with MS be best supported to self-manage their condition?

Recruitment:

We plan to recruit from the outpatient MS clinics at Leeds Teaching Hospitals NHS Trust and University College London. We will explain to PwMS that this is a small study called a pilot trial. They may have no personal benefit at all from taking part in the study. If the study is successful it may lead to a much larger trial of READY for MS.

We have previous experience in Leeds of recruiting over 200 employed PwMS to a previous MS Society funded project grant. This required the completion of questionnaires at 4 time points over 2 years. We had a very impressive response rate at each time point of 96%, 94%, 91% and 88%.

Inclusion and Exclusion criteria:

To be included in the trial people need to have a confirmed diagnosis of MS and currently be in paid employment (full-time, part-time or self-employed). We plan to screen PwMS with a short screening questionnaire called the Work Instability Scale. This measures the level of work instability as no/moderate or high. Work instability measures the potential risk of job loss. Participants with moderate or high work instability will be invited to be randomised in the trial. Those with no work instability will not be included in the

IRAS 279736

trial. The reason for this is that the trial is measuring work instability as the main outcome with an aim to show improvement.

PwMS who are currently working on a voluntary basis or in an unpaid role will not be eligible for the trial.

PwMS who are planning to fully leave work or retire before the end of the trial will be excluded.

Consent

PwMS who are currently employed will be approached by their clinical MS team including the MS Specialist nurses and MS specialist neurologists. The clinical team will introduce the study to the potential participants.

Those PwMS who say that they would potentially be interested in the study will be asked if their details can be given to the research team to provide written information about the study for them to consider (the Participant Information Sheet). The consent process will be completed by the research team.

We are recruiting PwMS in paid employment to this study and we anticipate that this study population will have capacity to consent. We don't anticipate that this employed population will have significant cognitive impairment.

Confidentiality

All the investigators in the study will comply with the requirements of the Data Protection Act 2018, and by extension the principles of the GDPR 2018.

All the participants' data will be depersonalised, coded and then stored electronically in password protected files. There will be an encrypted digital copy of the original files kept in separate storage media. The data will be processed and stored for the duration of the study and thereafter for the purposes of any follow-up. Access to the data will be limited to the minimum number of individuals necessary for quality control, audit and analysis.

Conflict of interest

There are no conflicts of interest for the health care professionals who are investigators in this study. [name] developed READY for MS. This study is a non-commercial NHS based study.

All the data collected will be held in accordance with the GDPR 2018 regulations and any pertinent clinical information will be relayed to the clinical team looking after the participant with their consent.

6.1 Assessment and management of risk

PwMS who are excluded at screening due to having no work instability may feel disappointed at not being able to participate in the trial. We will explain that the main purpose of the trial is to find out if we can measure an effect on work instability and if they have no work instability to start with then no improvement in this can be measured.

There is a risk that completing the online sessions and workbook of READY for MS may highlight work related problems or other problems related to living with MS. The MS specialist nurses will provide both planned support and flexible support as required including signposting. Any significant issues involving psychological distress will be escalated according to the local pathways of care. This would include informing the GP and appropriate psychological support. READY for MS has been designed to improve resilience and the ability to cope with day to day life challenges. However, we acknowledge that there may be unintended consequences.

The benefit of participating in the study is that this research addresses one of the key priorities of the MS Society in improving self-management of MS. Although this study will not lead to any personal benefit it may lead to a larger trial and potentially an effective treatment in the future.

During the study the participant will be reminded of their right to withdraw from the study at any point, without the need to provide an explanation and the PIS will include the Project Manager's contact details for all queries throughout the duration of the study.

